10.4 Baseline Value and Change from Baseline

For all safety variables that involve eCRF data collected during study visits prior to the first dose of study drug, the baseline value is defined as the last non-missing value obtained immediately prior to the first dose.

Change from baseline variables will be calculated by subtracting the baseline value from the post-baseline derived visit (i.e., for derived Visit 3 to Visit 15 as per table in [Section 11.4](#)) for each subject.

11 SUBJECT DISPOSITION, BASELINE CHARACTERISTICS, AND EXPOSURE

11.1 Subject Disposition

Subject disposition will be summarized by safety evaluable subgroups, overall, and by country.

The number and percentage of subjects who discontinued the study along with the distribution of the reasons for discontinuation will be presented overall and by safety evaluable subgroups.

Since the protocol allows for subjects who are benefiting from treatment with YKP3089 to continue the use of the drug at the discretion of the investigator, until development is stopped by SK Life Science Inc or the product is approved for marketing, or anytime at the discretion of SK Life Science Inc., study completion is included as an option for reasons for discontinuation on eCRF.

For any interim reporting of the results from this study, number of subjects ongoing at the time of interim date of data cut-off will be presented overall and by safety evaluable subgroups.

The number and percentage of subjects in each analysis population will be presented overall, by safety evaluable subgroups (when applicable), by country, and by geographic region.

For subjects who are screen failures, reason for screen failures will be listed in enrollment status listing.

For summary tables the reasons for termination/withdrawal will be summarized for the following categories: adverse event, lost to follow-up, pregnancy, protocol deviation, withdrew consent for reason other than adverse event, other reason, and completed.

By-subject data listings will include reason for termination/withdrawal as recorded on eCRF.

11.2 Protocol Deviations

Protocol deviations will be recorded by monitoring CRO (PPD) and recorded in their tracking system by deviation category. Protocol deviations will be included in a by-subject listing for subjects in safety population.

11.3 Demographic and Baseline Characteristics

The following demographic and other baseline characteristics will be summarized overall and by safety evaluable subgroups in safety population:

- Sex
- Age (years)
- Age groups (18-64 years, >=65 years)
- Race
- Ethnicity
- Weight (kg)
- Height (cm)
- Body Mass Index (BMI) (kg/m²)

Summary results will include number and percentages (sex, age groups, race, and ethnicity) and mean, standard deviation (SD), median, minimum, maximum (age, weight, height, BMI).

By-subject listings of all baseline characteristics (including childbearing potential) will be generate for all enrolled subjects. A separate listing for demographic characteristics (including childbearing potential) will be prepared for screen failures.

11.4 Drug Exposure, Dosing, and Compliance

The extent of exposure to study drug (YKP3089 and concomitant AED) as recorded on eCRF will be provided in a listing by-subject and by visit.

Drug exposure will be summarized for exposure to YKP3089 (throughout the entire duration of the study for all 3 safety evaluable subgroups) and Phenytoin and Phenobarbital dosing during titration period (including only corresponding safety evaluable subgroups: subjects taking phenytoin and YKP3089, subjects taking phenobarbital and YKP3089, respectively).

The following parameters will be derived for each subject in the ~~ITT~~/safety population:

- Number of days/weeks/months YKP3089 study drug medication was taken

- Number of days on each YKP3089 dose level (12.5 mg up to an including 400 mg or maximum reported daily dose) during the titration phase, the maintenance phase and overall during study.
- Modal YKP3089 daily dose defined as the dose taken the most days during maintenance phase (Visit 9 to Visit 14); in case of ties (i.e., 2 different dose levels taken the same number of days), modal dose will be defined as the highest dose between the two.
- Daily phenytoin dose during titration phase (for subjects taking phenytoin and YKP3089 only)
- Daily phenobarbital dose during titration phase (for subjects taking phenobarbital and YKP3089 only)

11.4.1 Exposure to YKP3089 study drug

The following will be summarized overall and by safety evaluable subgroups:

- Length of exposure (weeks and months)
- Number and percentages of subjects by time intervals (0-<1 weeks, 1-<2 weeks, 2-<4 weeks, 4 - <12 weeks, 12 - <24 weeks, 24-<48 weeks, 48-<96 weeks, >=96 weeks)
- Number and percentage of subjects by exposure categories: >= 1 dose, >=6 months, >=12 months, >=18 months, >=24 months, >=36 months

For any interim reporting of the results from this study, only applicable exposure categories based on maximum duration of exposure observed will be included in the summary tables).

Derivation for length of exposure to YKP3089:

- Length of exposure to YKP3089 (days) = (stop date – start date + 1).
- Length of exposure to YKP3089 (weeks) = length of exposure to YKP3089 (days)/7
- Length of exposure to YKP3089 (months) = length of exposure to YKP3089 (days)/30.4

Start and stop dates are define as per rules below:

Analysis Period	Subject Participation	
	Enrolled and discontinued study	Enrolled and ongoing at date of data cut-off
Overall	Start Date = First dose date Stop Date = last dose date	Start date = First dose date Stop Date = date of data cut-off
Titration Phase	Start date = First dose date Stop Date = Visit 9 date OR Last dose date	Start date = First dose date Stop Date = Visit 9 date OR date of data cut-off
Maintenance Phase	Start Date = Visit 9 date + 1 Stop Date = Last dose date	Start Date = Visit 9 date + 1 Stop Date = date of data cut-off

Descriptive statistics (mean, standard deviation, median, minimum, and maximum) will be provided to summarize the length of exposure (in weeks and in months) for each safety evaluable subgroup and overall. Similar summary results will be prepared by modal dose within each safety evaluable subgroup.

The number and percentage of subjects at each dose level will be summarized by safety evaluable subgroup and overall for the titration phase, the maintenance phase and overall during study. The length of exposure to YKP3089 at each dose level (from 12.5 mg up to maximum daily dose reported in study) will be summarized using descriptive statistics (mean, standard deviation, median, minimum, and maximum).

Dosing duration will also be expressed in terms of total subject years of exposure to YKP3089, calculated as the sum of all subject exposure days, divided by 365.25.

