6.2 Study Endpoints

6.2.1 *Pharmacokinetic Endpoints*

Sparse PK blood samples will be collected to evaluate YKP3089 and relevant concomitant AED exposure using a population pharmacokinetics approach. This will allow for the investigation of potential effects of covariates on the pharmacokinetics of YKP3089 or other concomitant AEDs. YKP3089 and other concomitant plasma concentration data collected from this study will be pooled with relevant data from other YKP3089 clinical studies for population PK analysis.

6.2.2 *Safety Endpoints*

Safety will be assessed by the nature, frequency, and severity of treatment-emergent spontaneously reported AEs, dropouts due to AEs, overall dropout rates, and changes from baseline in vital signs, physical exams, clinical laboratory evaluations, C-SSRS and 12-lead ECGs, in YKP3089-treated subjects.

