7.2 Safety Endpoints

Safety endpoints will include:

- Exposure (YKP3089 and concomitant phenytoin /phenobarbital AEDs)
- Adverse events (treatment emergent, serious adverse events, discontinuations due to adverse events)
- Overall discontinuation rates
- Concomitant Medications
- Vital signs
- Physical exams
- Clinical laboratory evaluations

- Columbia Suicide Severity Rating Scale (C-SSRS)
- 12-lead ECGs

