14 INTERIM ANALYSIS

An early data cut-off may be applied for the purpose for regulatory safety reporting. The date for the early data cut-off will be noted in the summary tables and in by-subject listings.

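### Overall discontinuation, a named safety endpoint, is planned only as a crude percentage over unequal follow-up and so is not a risk at any defined time

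*SAP*

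**What the plan says.** Protocol 6.2.2 lists among its safety endpoints "dropouts due to AEs, overall dropout rates, and changes from baseline in vital signs". SAP 7.2 carries this over as "Overall discontinuation rates".

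The analysis is in SAP 11.1: "The number and percentage of subjects who discontinued the study along with the distribution of the reasons for discontinuation will be presented overall", and also by AED subgroup. For an interim report it adds that the "number of subjects ongoing at the time of interim date of data cut-off will be presented overall and by safety evaluable subgroups". Completion is one of the seven summary categories for termination. The SAP explains that it is an option on the case report form because subjects who benefit may stay on drug until the sponsor ends development, the product is approved, or the sponsor decides otherwise.

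On timing, SAP 14 says: "An early data cut-off may be applied for the purpose for regulatory safety reporting".

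SAP 11.4.1 describes exposure separately: "Number and percentage of subjects by exposure categories: >= 1 dose, >=6 months, >=12 months, >=18 months, >=24 months, >=36 months". For subjects still on drug, "Stop Date = date of data cut-off". Its one interim rule for the categories is that "only applicable exposure categories based on maximum duration of exposure observed will be included in the summary tables". The same section plans length-of-exposure statistics and total subject-years.

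SAP 10.1 limits the whole plan to description. Neither document plans a time-to-discontinuation estimate, a discontinuation rate per subject-year, or a percentage restricted to subjects who could have reached a given time.

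**The concern.** A percentage of subjects who have discontinued is a risk only when everyone has been followed for the same time, or when the time is stated. Here a subject dosed for two weeks and still on drug counts as not discontinued, exactly like one dosed for two years and still on drug. The number ongoing does not separate them. The percentage therefore reflects both how readily subjects stop and how long they happen to have been followed, and the second part is set by accrual and the cut-off date.

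The difficulty can outlast the interim. At final reporting, subjects whose treatment ends administratively have different durations, and completion appears among the reasons for leaving. The breakdown by reason shows them, but it still ties the overall figure to no time point.

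At stake is whether the report can say what proportion of subjects stop YKP3089 by 6, 12 or 24 months. Without that, discontinuation cannot be compared across cut-offs of this study or with another study.

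**Working it through.** The documents give no accrual period, cut-off date, dropout rate or retention figure, so the plan has no figure to reproduce. Everything below is illustration under stated assumptions.

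**1. What the crude percentage estimates.** Let F be a subject's time from first dose to cut-off and h a constant monthly discontinuation hazard.
- Risk by time t: 1 − exp(−h·t).
- Expected crude percentage: the average of 1 − exp(−h·F) over subjects, which depends on the distribution of F.

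**2. Assumed inputs.**
- Annual dropout of 15% or 30%: h = −ln(0.85)/12 = 0.01354, or −ln(0.70)/12 = 0.02972.
- Uniform accrual over A = 12, 18 or 24 months, with the cut-off 6 months after the last first dose. F is then uniform from 6 to 6 + A months.

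Crude percentage = 1 − [exp(−6h) − exp(−(6+A)h)]/(A·h).

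For A = 12 and 15% dropout: 1 − (0.9220 − 0.7837)/0.1625 = 1 − 0.851 = 14.9%.

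| Accrual A | Mean F | Crude, 15%/yr | Risk at mean F, 15%/yr | Crude, 30%/yr |
|---|---|---|---|---|
| 12 mo | 12 mo | 14.9% | 15.0% | 29.6% |
| 18 mo | 15 mo | 18.2% | 18.4% | 35.2% |
| 24 mo | 18 mo | 21.3% | 21.6% | 40.2% |

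In all three rows the 6-month risk is 7.8% (15% per year) or 16.3% (30% per year), and the 12-month risk is 15.0% or 30.0%.

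**3. The same question in reverse.** An observed crude 20% corresponds to 12-month retention of:
- 79.3% with accrual over 24 months and cut-off at month 24 from the first subject's first dose;
- 79.8% with 12 and 18 months;
- 83.4% with 18 and 24 months;
- 89.4% with 12 and 30 months.

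One reported figure thus fits a 12-month discontinuation risk anywhere from 10.6% to 20.7%.

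**4. Exposure rows.** The share with at least t months of exposure is P(F ≥ t) × retention at t. Under the step 2 accruals, P(F ≥ 12) is 50%, 67% or 75%. With 85% retention the row for 12 months or more reads 0.50 × 85 = 42.5%, 56.7% or 63.8%. With 70% retention it reads 35.0%, 46.7% or 52.5%. Now put the cut-off 36 months after the first subject's first dose, with accrual of at most 24 months. Everyone has F of at least 36 − 24 = 12 months, P(F ≥ 12) = 1, and the row equals retention.

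**5. Does a censored estimate fix it?** The check used 500 simulated trials of an assumed 1,300 subjects, 80% retention at 12 months, accrual over 18 months and cut-off at month 24. The mean Kaplan-Meier retention at 12 months was 80.0%. The crude discontinuation percentage was 24.1% (24.0% by formula), which matches neither the 12-month risk of 20% nor the 24-month risk of 36%.

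**The case against.** **The crude rate is not biased; it rises because follow-up is longer.** This is fair. In the table it stays within 0.3 percentage points of the risk at mean follow-up. But the plan does not report mean potential follow-up or tie the percentage to it, so the reader cannot tell which time point the figure approximates.

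**Subject-years are planned.** Under a constant hazard, discontinuations divided by subject-years recover the rate whatever the accrual: 12 × 0.01354 = 0.1625 per year, and 1 − exp(−0.1625) = 15.0%. That narrows the gap. But the SAP does not print the ratio, dropout need not be constant over time, and a single rate does not give retention at a time point.

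**The early cut-off is optional, and the table shells are separate documents.** Both are true. The SAP also does not write out the denominators. All subjects in the reporting group is the natural reading, since the exposure rows begin at one dose or more and no other denominator is defined.

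Three stronger readings are tempting but not supported:

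- *A reader might infer that the exposure percentages are wrong or understate persistence.* They describe exposure accrued by the cut-off and are correct as such, as is the count of at least 1,000 subjects exposed for 6 months. Neither document defines a retention endpoint. They mislead only if read as retention.
- *A reader might infer that the AED subgroups were enrolled at different times, so that the crude rate distorts comparisons between them.* Staged enrolment appears only as superseded text in the protocol's summary of changes. The current text does not stage it.
- *A reader might infer that long-term safety is the main objective.* It is the third of four listed evaluations.

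**Conclusion.** The point holds for the discontinuation endpoint. As planned, it is a crude percentage over unequal follow-up and is not a risk at any defined time. Under the illustrative assumptions, a constant 12-month risk of 15% would be reported as 14.9% to 21.3%, and one of 30% as 29.6% to 40.2%, depending only on accrual. These ranges rest on uniform accrual, a constant hazard and a cut-off 6 months after the last first dose, none of which is in the documents.

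For the exposure table the point is one of interpretation. The gap between its percentages and retention depends on the cut-off, and is zero for any row that every subject could have reached.

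This is an inexpensive improvement to a stated endpoint, not a flaw that invalidates the planned tables.

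**What to change.** In SAP 11.1, add a descriptive Kaplan-Meier summary of time from first dose to study drug discontinuation, overall and for the three safety subgroups.

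- Censor subjects still on drug at the data cut-off date. Censor those ended administratively (completion, sponsor decision or approval) at the date this happened.
- State how the termination categories map to event or censoring. In particular, say how a subject who leaves at the 12-month evaluation for lack of benefit is coded, since that is not an administrative end.
- Report cumulative discontinuation at 6, 12, 18 and 24 months, and at 36 if reached, with numbers at risk.

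Keep the SAP 11.4.1 exposure table unchanged. Add a footnote that its percentages are exposure accrued by the cut-off and not retention.

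Two supplements are optional: exposure percentages based only on subjects first dosed at least that long before the cut-off, and a cumulative incidence of discontinuation due to adverse events with other reasons as competing events.

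The cost is one extra table and a footnote. The first-dose, last-dose, reason and cut-off dates are already needed for the planned tables, so no new data are required. The summary is descriptive and fits SAP 10.1.

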6 STUDY DESIGN AND VISIT SCHEDULE

This is a multicenter, open label study in subjects with poorly controlled partial seizures. The study will consist of a:

- screening period,
- open-label titration phase,
- open label maintenance phase
- taper and follow up.

The study will enroll:

- Subjects on stable doses of phenytoin
- Subjects on stable doses of phenobarbital
- Subjects on stable doses of other concomitant AEDs

from approximately 80-110 sites (US and other countries)t

At least 20 subjects taking phenytoin and at least 20 subjects taking phenobarbital are to be enrolled. Additional subjects taking AEDs other than phenytoin or phenobarbital are to be enrolled in order to expose at least 1,000 subjects for 6 months to further evaluate long term safety.

Details about inclusion / exclusion criteria are included in Protocol Sections 7.3 and 7.4.

The screening period for subjects on stable doses of phenytoin or stable doses of phenobarbital or stable doses of other concomitant AEDs will be up to 21 days.

The open label treatment period will consist of a 12 week titration phase followed by an open label maintenance phase.

The titration phase for subjects on stable doses of phenytoin or stable doses of phenobarbital will be 12 weeks. During the 12-week up-titration phase, subjects will increase YKP3089 dose every 2 weeks to a target dose of 200 mg/day as described in the table below:

Table 1. YKP3089 Initial Up-Titration for subjects on phenytoin and phenobarbital

YKP3089 dose (mg/day)					
Week 1 & 2	Week 3 & 4	Week 5 & 6	Week 7 & 8	Week 9 & 10	Week 11 & 12
12.5	25	50	100	150	200

The titration phase for subjects on stable doses of other concomitant AEDs will be 12 weeks. Increasing doses of YKP3089 will be administered (50, 100, 150 and 200 mg/day) at 2-week intervals as described in the table below:

Table 2. YKP3089 Initial Up-Titration for subjects on concomitant AEDs other than phenytoin or phenobarbital

YKP3089 dose (mg/day)					
Week 1 & 2	Week 3 & 4	Week 5 & 6	Week 7 & 8	Week 9 & 10	Week 11 & 12
12.5	25	50	100	150	200

During titration phase, the investigator may add, remove, or adjust the dosage of any concomitant AEDs, as clinically indicated:

Table 3. Dose Adjustment Rules during Titration Phase

Cohort →	Subjects taking Phenytoin or Phenobarbital	Subjects taking AEDs other than Phenytoin or Phenobarbital
Adjustments of any Concomitant AEDs	Not Allowed	Allowed
Adjustments of YKP3089	Not Allowed	Allowed

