Adjustment of Phenytoin or Phenobarbital	Allowed	Not Applicable

Monotherapy with YKP3089 will not be allowed. If clinically indicated, titration can be stopped below 200 mg/day. A minimum dose of 50 mg/day is necessary to continue in the study.

During open label maintenance phase:

- (1) For subjects taking phenytoin or phenobarbital, the initial target dose will be 200 mg/day. If the investigator feels that a subject requires a dose that is higher than 200 mg/day, the dose can be increased to a maximum of 400 mg/day once the target dose of 200 mg/day was reached. The upward dose adjustments should occur every other week in increments of 50-mg/day. If the investigator feels that a subject requires a dose that is lower than 200 mg/day, the dose can be reduced to a minimum of 50 mg/day once the target dose of 200 mg/day was reached. The downward dose adjustments may occur weekly by 100 mg/day or 50 mg/day.
- (2) For subjects taking other concomitant AEDs, the initial target dose will be 200 mg/day. If the investigator feels that a subject requires a dose that is higher than 200 mg/day, the dose can be increased to a maximum of 400 mg/day once the target dose of 200 mg/day was reached. The upward dose adjustments should occur every other week in increments of 50 mg/day. If the investigator feels that a subject requires a dose that is lower than 200 mg/day, the dose can be reduced to a minimum of 50 mg/day once the target dose of 200 mg/day was reached. The downward dose adjustments may occur weekly by 100 mg/day or 50 mg/day.
- (3) The investigator may add (except phenytoin or phenobarbital), remove, or adjust the dosage of any concomitant AEDs, as clinically indicated:

Table 4. Dose Adjustment Rules during Maintenance Phase

Cohort →	Subjects taking Phenytoin or Phenobarbital	Subjects taking AEDs other than Phenytoin or Phenobarbital
Adjustments of any Concomitant AEDs	Allowed	Allowed
Adjustments of YKP3089	Allowed	Allowed
Adjustment of Phenytoin or Phenobarbital	Allowed	Not Applicable

Subjects who are withdrawn from the open-label treatment period will taper YKP3089 according to the schedule described in [Table 5](#), unless for safety reasons the investigator judges it necessary to discontinue study drug immediately.

Table 5. Study Drug Taper Schedule for Subjects Completing Open-Label Treatment

Final open-label dose of YKP3089 (mg/day)	YKP3089 Dose During Taper (mg/day)		
	Week 1	Week 2	Week 3
50 or 100	None		
150 or 200	100	None	None

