8 STUDY PROCEDURES AND ASSESSMENTS

The study will include multiple study visits during the 3 years duration. Titration phase will include 7 study visits (Visit 2 to Visit 8), Maintenance phase will include up to 5 visits (Visit 9 to Visit 14). Visit 15 is considered 14-days after last dose follow-up visit. Subjects who benefit from treatment, may continue in an Open-Label Extension beyond year one with visits occurring every 3 months.

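### The SAP's exposure rules end the 12-week titration phase at Visit 9 (nominal Day 99), and its visit windows leave days 1 to 13 after the last dose in no derived visit

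*SAP*

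**What the plan says.** **Phase boundary.** SAP 6 states: "The open label treatment period will consist of a 12 week titration phase followed by an open label maintenance phase". It repeats the length for the phenytoin/phenobarbital cohort: "The titration phase for subjects on stable doses of phenytoin or stable doses of phenobarbital will be 12 weeks". SAP 8 allocates the visits: "Titration phase will include 7 study visits (Visit 2 to Visit 8"), then "Maintenance phase will include up to 5 visits (Visit 9 to Visit 14"). The column heads of the Appendix 1 flowchart make the same split.

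The analysis sections use a different boundary. For titration exposure in subjects who have discontinued, SAP 11.4.1 gives "Stop Date = Visit 9 date OR Last dose date", with the data cut-off replacing the last dose for ongoing subjects. For maintenance it gives "Start Date = Visit 9 date + 1". SAP 11.4.2 also names Visit 9 as the end of titration for the phenytoin and phenobarbital dose summaries. SAP 11.4 takes the modal dose over a maintenance phase that starts at Visit 9.

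**Follow-up window.** In the SAP 10.3 table for laboratory tests, vital signs and C-SSRS, footnote [2] limits the treatment-period windows to days no later than the last dose. The Visit 15 row opens at last dose +14, which is also its target day. SAP 13.1 counts TEAEs through last dose +14.

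**The concern.** Two tabulation rules do not match what they are meant to describe.

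First, about two weeks that SAP 6 and SAP 8 call maintenance are tabulated as titration. This touches exposure by phase, dose level by phase, and the end-of-titration phenytoin/phenobarbital dose tables. The label has content for the phenytoin/phenobarbital cohort: under "Table 3. Dose Adjustment Rules during Titration Phase" YKP3089 adjustments are not allowed, and under "Table 4. Dose Adjustment Rules during Maintenance Phase" they are. An adjustment made under the maintenance rules between Visit 8 and Visit 9 would appear as a titration dose level. SAP 4 says that substantial differences from the protocol are identified, but SAP 16 does not mention a Visit 9 boundary.

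Second, valid post-dose values drop out of the by-visit, change-from-baseline and by-timepoint shift tables, although adverse events in the same days are counted. The days are not empty by design. Protocol 9.3 provides for immediate discontinuation in some suspected hypersensitivity cases, and any unscheduled laboratory values taken after such a stop would fall here.

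The overall laboratory shift table in SAP 13.2 is not a clean fallback. It is introduced as covering all post-baseline results, yet its *normal* category is limited to the treatment period and its *abnormal* category is not.

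**Working it through.** **Inputs**
- Six dose steps of two weeks each (SAP 6, Tables 1 and 2); 200 mg/day starts in Week 11, which is Day 71.
- Visit 8 is Day 85 and Visit 9 is Day 99 (protocol 9.1.8 and 9.1.9). Visits 3 to 10 have a window of ±2 days (protocol 9).
- The first dose may be taken on the day of Visit 2 or the next morning (protocol 9.1.2).
- Exposure in days = stop − start + 1 (SAP 11.4.1).

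**The plan's own figure.** 6 × 14 = 84 days = 12 weeks, ending on Day 84. Visit 8 on Day 85 fits this.

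**Titration exposure for a subject on schedule**

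| First dose | Stop at Visit 9 (SAP 11.4.1) | Stop at Visit 8 | Difference |
|---|---|---|---|
| Day of Visit 2 | 99 − 1 + 1 = 99 days; 99/7 = 14.1 weeks | 85 − 1 + 1 = 85 days; 85/7 = 12.1 weeks | 14 days; 14/85 = 16.5% |
| Next morning | 98 days | 84 days | 14 days; 14/84 = 16.7% |

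Against exactly 84 days, the 99 days are an excess of 15.

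**Range over the visit windows.** Visit 8 may fall on Days 83 to 87 and Visit 9 on Days 97 to 101.
- Smallest shift: 97 − 87 = 10 days; 10/87 = 11.5%.
- Largest shift: 101 − 83 = 18 days; 18/83 = 21.7%, or 18/82 = 22.0% if the first dose is the next morning.

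**Days at 200 mg/day labelled titration, if the dose is held**
- To Visit 9: 99 − 71 + 1 = 29 days.
- To Visit 8: 85 − 71 + 1 = 15 days (14 days if titration ends on Day 84).

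**Maintenance exposure to Day 365**
- From Day 100: 365 − 100 + 1 = 266 days.
- From Day 86: 365 − 86 + 1 = 280 days.
- Difference: −14 days; −14/280 = −5.0%.

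**Consistency within the SAP.** The modal-dose period opens at Visit 9 (Day 99) and maintenance exposure at Visit 9 + 1 (Day 100), so these two differ by one day at most. Visits 9 to 14 are six visits where SAP 8 says up to five. Five would fit a reading in which Visit 9 closes titration, so SAP 8 is itself unclear.

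**Follow-up window.** Let L be the last-dose day and d = L + k the assessment day.
- A treatment-period window needs d ≤ L, so k ≤ 0.
- Visit 15 needs d ≥ L + 14, so k ≥ 14.
- No row accepts k = 1 to 13. Applying the table to every L from Day 1 to Day 1112 gives the same answer each time.
- TEAEs count on k = 1 to 14, so 13 of those 14 days have no derived visit.
- Assumption: if the protocol's ±7 days for other open-label visits covers Visit 15 (the text does not say), the permitted days are +7 to +21, which is 15 days. Seven of them (+7 to +13) are unassigned; 7/15 = 46.7%. If it does not, an early Visit 15 is a deviation and is still unassigned.

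The ECG and physical examination tables carry the same rule. Visit 15 schedules neither, so only Termination or unscheduled assessments could be affected there. The Termination row is tied to the treatment period, so it is unclear whether it accepts a Termination Visit held after the last dose.

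**SAP 13.2.** Read literally, a subject whose only abnormal value comes after the last dose has none in the treatment period and at least one post-baseline, and so meets both definitions.

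**The case against.** On the phase boundary, the analysis sections agree on Visit 9 to within a day, the date rules are explicit, and the output is reproducible; the conflict is with descriptive text. Visit 9 is also defensible. The last phenytoin/phenobarbital draw is at Visit 8, so a dose change prompted by it would first be recorded at Visit 9. The rule conflict between Tables 3 and 4 concerns only the phenytoin/phenobarbital cohort, with planned minimums of 20 and 20 in a study meant to expose at least 1,000. All of this stands as a reason to allow Visit 9. It does not remove the contradiction, because nowhere does the SAP say that its analysis phase is about 14 weeks long.

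On the follow-up window, Visit 15 is scheduled for day +14, inside its window, and for tapered subjects the Termination Visit comes before the taper. The gap therefore catches early Visit 15s, Termination Visits after dosing has stopped, and unscheduled visits; the count of 13 days in 14 describes the rule and not the share of data lost. Listings keep every value, and the anytime summaries for liver tests, vital signs and C-SSRS can capture them. This limits the size but leaves the fault: a Visit 15 one day early is excluded. For haematology and non-liver chemistry the only anytime summary table is the overall shift table. One could read its treatment-period limit as governing both categories, but the wording does not secure that.

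**Conclusion.** Both points hold, and both are minor.

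The first mislabels about two weeks per subject. The shift is 14 days on schedule and 10 to 18 days within the visit windows, and it applies to subjects who reach Visit 9; those who stop between the two visits lose correspondingly fewer maintenance days, and those who stop by Visit 8 are unaffected. The figures for days at 200 mg/day assume that the dose is held. The second leaves by-visit safety tables incomplete for days +1 to +13. The figure of 7 days in 15 depends on the ±7-day assumption; the gap itself does not. The number of subjects affected cannot be derived from the documents.

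Total exposure, the 6- and 12-month counts, subject-years and TEAEs are untouched. SAP 10.1 rules out inferential analysis, so the result would be mislabelled or incomplete tables and not a wrong inference.

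**What to change.** **Phase boundary.** Use one boundary in SAP 8, 11.4, 11.4.1 and 11.4.2, by either route:
- Use the Visit 8 date (or the last dose or data cut-off, if earlier) for by-phase exposure and the end-of-titration dose, and show the Visit 9 phenytoin/phenobarbital dose by visit as the first maintenance value. Cost: a change first recorded at Visit 9 leaves the end-of-titration summaries and the counts of subjects with any increase or decrease, and remains only in the by-visit rows.
- Keep Visit 9, state that the analysis titration phase runs to Visit 9 (about 14 weeks), label the tables accordingly and correct the visit lists in SAP 8. Cost: the analysis phase then differs openly from the 12-week design phase.

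**Follow-up window.** Open Visit 15 at last dose +1, select the value nearest +14, and label the row post-treatment follow-up. A small drawback is that an early post-dose value fills the row when it is the only one available.

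**SAP 13.2.** Apply the same period, including results after the last dose, to both *normal* and *abnormal* so that no subject can meet both.

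These are SAP wording and derivation changes only; no new data are needed.
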